## COPD Population Definition

The Global Initiative for Chronic Lung Disease (GOLD) formed in 1998 and released a consensus report titled *Global Strategy for the Diagnosis, Management, and Prevention of COPD* (GOLD, 2011). This report was revised in 2006 and 2011, and is widely recognized among health care professionals, researchers, and other stakeholders. GOLD has published criteria used to diagnose COPD, and recommends the use of post-bronchodilator spirometry data to grade the severity of COPD to minimize variability in measurements. Only pre-bronchodilator spirometric data is available in all studies in this analysis, however, and therefore will be evaluated as to its suitability in defining COPD. Specifically, analyses will quantify the difference between pre- and post-bronchodilator spirometry in ECLIPSE to quantify any potential misclassification that may arise from using pre-bronchodilator spirometric data. Sensitivity analyses will be performed to compare the patient population defined at FEV1 levels of 60% and 70% to those meeting the criteria for GOLD stage 2 and above.

The following GOLD COPD severity definitions will be used in analyses:

1. Gold Stage 2: FEV1/FVC <0.70 and FEV1 50–79% of normal
2. Gold Stage 3: FEV1/FVC <0.70 and FEV1 30–49% of normal
3. Gold Stage 4: FEV1/FVC <0.70 and FEV1 <30% of normal
  - a. Note: Stage 4 also includes patients with a FEV1 <50% of normal with chronic respiratory failure present but the data does not allow for determining if chronic respiratory failure is present. Therefore, it will not be included in the definition used in SAP.

The following definitions for COPD will be used for all analyses among patients with at least one fibrinogen result unless otherwise stated:

1. COPD patients will be defined as those  $\geq 40$  years of age with moderate, severe, or very severe COPD, as defined by meeting the criteria for GOLD Stage 2+, as described above.
2. A second COPD definition will include the above criteria (i.e., age  $\geq 40$  years, GOLD stage 2+), but include only patients with a history of COPD exacerbations to identify a patient sample that is similar to those used in clinical trials of medications developed to treat COPD. This definition can only be used in ECLIPSE, however, as other studies did not collect history of prior COPD exacerbations.

FEV1 predicted and FEV1 % predicted values were not provided within the NHANES and FHS datasets. FEV1 predicted values were calculated using the equations published by Hankinson et al (1999). Race and ethnicity information was not captured in the FHS dataset but all three Framingham Cohorts (Original Cohort, Offspring Cohort, and Third-Generation Cohort) have been characterized as predominantly white (Splansky et al., 2007); therefore, the prediction equation for Caucasians was used for all patients in FHS. Race/ethnicity was captured in the NHANES data as 'white' vs. 'non-white'; therefore, the prediction

equation for Caucasians was used for NHANES patients characterized as 'white', and the prediction equation for African Americans was used for NHANES patients characterized as 'non-white'.

## Fibrinogen Classification

Based on preliminary analyses of the distribution of fibrinogen among patients with COPD, four thresholds of baseline fibrinogen will be assessed in these analyses: 250 mg/dL, 300 mg/dL, 350 mg/dL, and 400 mg/dL. The terms "high" and "low" fibrinogen will refer to the level of fibrinogen in relation to the threshold(s) being assessed in the analysis.

## Outcome Ascertainment

Exacerbations and other clinical events were recorded differently in each study depending on the study objectives and population. In ARIC and CHS, exacerbations were identified as hospitalizations with an International Classification of Diseases, 9th Revision, Clinical Modification (ICD-9-CM) code of (490.x, 491.x, 492.x and 496.x) in any position (principal or supporting diagnosis). In ECLIPSE, hospitalized COPD exacerbations were recorded in the supplemental clinical event file as 'EXACHOSP'. COPD exacerbations were not recorded outcomes in NHANES or FHS. All-cause mortality was recorded in each study in the integrated database.

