## General Statistical Considerations

This is a retrospective database analysis of previously collected data from prospective clinical trials and observational studies. These data offer an opportunity to evaluate the relationship between plasma fibrinogen and adverse COPD outcomes by pooling data from multiple sources. Analyses will be conducted separately for individual studies and integrated as indicated. Data will be pooled across the

data sources as deemed appropriate for the analysis being conducted to uphold model assumptions and per variables available within each study.

Adverse COPD outcomes that will be assessed in these analyses include COPD exacerbations and all-cause mortality. The primary endpoint of clinical trials for COPD medications is a hospitalized COPD exacerbation; however, all-cause mortality does hold clinical importance in both the conduct of clinical trials and the overall management of any chronic disease.

As the data are analyzed, some deviation from the analyses outlined is anticipated (e.g., due to missing data; small sample sizes). In instances where these deviations would make the proposed analyses inappropriate, modifications to the analysis plan will be made in consultation with the CBQC and noted in the final report.

SAS statistical software version 9.2 (SAS Institute Inc., Cary, NC) will be used to conduct the analyses. All statistical tests will be two-sided and use a significance level of 0.05 unless otherwise noted. No adjustments for multiple comparisons will be performed unless otherwise noted. For all analyses, missing data will be considered randomly missing, and no data imputations or other algorithms for missing responses will be performed unless otherwise indicated. For certain procedures (such as analysis of variance) subjects with missing data will be excluded from the analysis.

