#### Supplemental data:

COPDGene: A prospective cohort study conducted at 21 sites in the United States. The COPDGene cohort includes 4,000 smoker controls with normal spirometry measurements (FEV1/FVC ratio  $\geq 0.7$ , FEV1  $\geq 80\%$  predicted), 2,000 patients meeting the criteria for GOLD stage 1 and GOLD stage unclassified (GOLD-U), 4,000 patients meeting the criteria for GOLD stages 2–4, and 100 non-smoker controls, for a total enrollment of 10,100 patients. Plasma fibrinogen was not collected in this study; therefore, data from this study will be used only to compare the diagnosis of patients using pre- and post-bronchodilator spirometry measurements, which were collected in the study.

Table 1. Study Population Information for Studies Proposed for Inclusion

Study	Study Population (n)	COPD Subjects (n)*	Longitudinal Fibrinogen Availability	Hospitalized COPD Exacerbations Within 12 months	Deaths within 3 Years among COPD Subjects
ARIC	15,462	1,789	No	96	86
CHS	5,730	1,292	No	236	120
ECLIPSE	2,726	2,118	Yes	335	220
Framingham Offspring Cohort	3,885	145	No	N/A	13
NHANES III	1,369	1,032	No	N/A	146

\* Aged ≥40 years and GOLD Stages 2, 3, or 4 – based on pre-bronchodilator spirometry

ARIC = Atherosclerosis Risk in Communities Study; CHS = Cardiovascular Health Study; COPD = chronic obstructive pulmonary disease; ECLIPSE = Evaluation of COPD Longitudinally to Identify Predictive Surrogate Endpoints; FHS = Framingham Heart Study; NHANES = National Health and Nutrition Examination Survey

Studies have been evaluated and integrated into one database for these analyses. Analyses described here will be conducted using both the individual study datasets and the full integrated dataset.

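### About half of the 12-month exacerbation events come from ARIC and CHS, where a COPD code in any diagnosis position counts and the cause of admission is not established; no analysis by code position is planned

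*SAP*

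**What the plan says.** The SAP, under General Statistical Considerations, ties the work to the endpoint used in drug trials: "The primary endpoint of clinical trials for COPD medications is a hospitalized COPD exacerbation".

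Outcome Ascertainment then gives two kinds of definition.

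- **ARIC and CHS:** a hospitalization with ICD-9-CM code 490.x, 491.x, 492.x or 496.x "in any position (principal or supporting diagnosis").
- **ECLIPSE:** a study-recorded event: "In ECLIPSE, hospitalized COPD exacerbations were recorded in the supplemental clinical event file as 'EXACHOSP'".
- **The other two studies:** "COPD exacerbations were not recorded outcomes in NHANES or FHS".

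The section acknowledges that events were recorded differently from study to study. It plans no analysis by code position and no validation of the coded events.

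Table 1 lists the events in a column headed "Hospitalized COPD Exacerbations Within 12 months". Analyses are to be run on each study and on the integrated dataset. In the last part of the SAP, the Cox models for each outcome supply the survival estimates for the sample sizes of a hypothetical trial.

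**The concern.** The analysed patients are GOLD stage 2 or above, so COPD can be expected as a listed comorbidity on some admissions for heart disease, fracture or surgery. The any-position rule turns each of these into a hospitalized exacerbation, and the integrated analysis puts them in one endpoint with the ECLIPSE events.

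Two results are at stake.

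- **The hazard ratio for fibrinogen.** If fibrinogen is unrelated to the other admissions, the ratio is diluted. If it is related to them, an association can appear where none exists for exacerbations. The SAP's Background cites a meta-analysis of fibrinogen and cardiovascular and non-cardiovascular mortality, so the second case is plausible.
- **The event rate.** Extra events raise the 12-month rate. A trial whose endpoint is a true hospitalized exacerbation would then be planned too small.

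**Working it through.** **Inputs (SAP, Table 1; columns are study population, COPD subjects, longitudinal fibrinogen, exacerbations, deaths)**

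- "ARIC 15,462 1,789 No 96 86"
- "CHS 5,730 1,292 No 236 120"
- "ECLIPSE 2,726 2,118 Yes 335 220"

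The SAP states only these counts. It gives no total, share or sample size for this outcome that could be reproduced.

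**Step 1. Share of events under the any-position rule**

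- Total: 96 + 236 + 335 = 667.
- ARIC and CHS: 96 + 236 = 332, and 332/667 = 49.8%.

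**Step 2. Misclassified share**

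Let f be the fraction of ARIC and CHS events that are not exacerbations. The documents do not give f, so it is varied. Misclassified share of all events: s = f × 332/667.

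**Step 3. Effect on the pooled hazard ratio**

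Observed HR ≈ (1 − s) × HR(exacerbation) + s × HR(other admissions). This treats s as the share in the low-fibrinogen group and takes the ECLIPSE events as correct. The component ratios are assumptions chosen for illustration. Case A: 1.0 for exacerbations and 1.3 for other admissions. Case B: 1.5 and 1.0.

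**Step 4. Effect on the pooled 12-month proportion**

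Taking Table 1 counts as patients among COPD subjects, the denominator is 1,789 + 1,292 + 2,118 = 5,199, and p = (667 − 332f)/5,199.

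**Step 5. Effect on the hypothetical trial**

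The SAP's settings are used: two-sided 0.05, power 0.80, equal arms, 10% loss. At a treatment hazard ratio of 0.7, the Schoenfeld formula requires 247 events. The treated-arm proportion is 1 − (1 − p)^0.7. Total N is 247 divided by the mean of the two arm proportions, then divided by 0.9.

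- f = 0: p = 0.1283, treated arm 0.0916, mean 0.1100. N = 2,247, or 2,497 with loss.
- f = 0.5: p = 0.0964, treated arm 0.0685, mean 0.0824. N = 2,997, or 3,330 with loss.

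| f | Misclassified events | s | HR, case A | HR, case B | p | Total N at HR 0.7 |
|---|---|---|---|---|---|---|
| 0 | 0 | 0% | 1.00 | 1.50 | 12.8% | 2,497 |
| 0.25 | 83 | 12.4% | 1.04 | 1.44 | 11.2% | 2,855 |
| 0.50 | 166 | 24.9% | 1.07 | 1.38 | 9.6% | 3,330 |
| 0.75 | 249 | 37.3% | 1.11 | 1.31 | 8.0% | 3,996 |
| 1.00 | 332 | 49.8% | 1.15 | 1.25 | 6.4% | 4,992 |

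At f = 0.5 the corresponding totals go from 1,297 to 1,732 at HR 0.6 and from 6,037 to 8,049 at HR 0.8.

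Within ARIC and CHS alone s equals f, so at f = 0.5 cases A and B give 1.15 and 1.25.

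The sample sizes illustrate the effect from a pooled crude proportion. They are not the SAP's figures, which will be given by fibrinogen threshold from the Cox models.

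**The case against.** **The plan already yields results free of the rule.** Analyses are run by study, pooling is left to judgement, and the second modelling group (prior exacerbation) is ECLIPSE only. This stands in part. ECLIPSE-only results will exist, but the Background justifies integration as evidence of robustness across populations. If ARIC and CHS measure a different outcome, neither agreement nor disagreement with ECLIPSE can be read as evidence about exacerbations.

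**COPD here is a spirometric classification.** ARIC and CHS are general-population cohorts, and low spirometry does not itself put a COPD code on a hospital record. This stands: how often incidental coding occurs cannot be known from the SAP.

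**The CHS rate.** A reader might infer over-counting from CHS, where 236/1,292 = 18.3% exceeds 335/2,118 = 15.8% in ECLIPSE, a cohort recruited with moderate to very severe COPD. The 3-year mortality runs the other way: 120/1,292 = 9.3% against 220/2,118 = 10.4%. The contrast does not establish over-counting:

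- ARIC uses the same rule and shows 96/1,789 = 5.4%.
- CHS enrolled people aged 65 and over.
- The exacerbation column, unlike the deaths column, is not labelled as restricted to COPD subjects and does not say whether it counts patients or events. With the study population as denominator, CHS is 236/5,730 = 4.1% and ECLIPSE 335/2,726 = 12.3%, and the contrast reverses.

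**Principal-only coding has its own error.** It loses true exacerbations coded second. This stands, and it is a reason to show both definitions rather than replace one by the other.

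**Conclusion.** The point holds as a gap in the plan. About half of the 12-month events (332 of 667, 49.8%) come from a rule that does not establish why the patient was admitted. They enter the integrated models and the sample-size exercise with no check by code position.

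A reader might infer that half of the events are admissions for something else. The SAP does not support that. The 49.8% is the share collected under the rule and so a ceiling, reached only if every ARIC and CHS event were false, including those with a principal COPD code. The true share is unknown, between 0 and 49.8%.

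At the illustrative midpoint, with half of the ARIC and CHS events incidental, 24.9% of all events are misclassified. A pooled true hazard ratio of 1.0 would then show as about 1.07 if other admissions carry 1.3, and a true 1.5 as about 1.38 if they carry 1.0. The pooled 12-month proportion falls from 12.8% to 9.6%, and illustrative total N at HR 0.7 rises by a third (3,330/2,497 = 1.33). These figures rest on the assumed f, the assumed component ratios and, for the proportions and N, the reading of Table 1 as patients among COPD subjects.

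**What to change.** 1. In Outcome Ascertainment, report ARIC and CHS events by code position, and state whether Table 1 counts patients or events and in which population.
2. Pre-specify a principal-position analysis of the exacerbation Cox models for ARIC, CHS and the integrated data, beside the any-position analysis.
3. In the sample-size section, show ECLIPSE-only and principal-position event rates, with the resulting sample sizes, beside the integrated ones.

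The main work is one re-derived variable and a repeat of planned models, provided code position is retained in the integrated database or can be retrieved from the source studies. The SAP does not say whether it is. If it cannot be had, state this as a limitation and keep the ECLIPSE-only sample sizes. The principal-position analysis will have fewer ARIC and CHS events and wider intervals, and will miss true exacerbations coded second.

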## Assay Methods

Several laboratory methods are available for the determination of plasma fibrinogen and these can be classified into two general categories:

1. *Functional methods* that measure "clottable" fibrinogen (Clauss method)
2. *Direct methods* that quantify the fibrinogen protein (Immunologic method)

In routine clinical laboratory practice, plasma fibrinogen is most commonly measured by a functional method that determines thrombin-clottable protein in plasma samples derived from whole blood collected with sodium citrate as the anticoagulant. These methods are based on the original method of Clauss and are frequently referred to as the Clauss or modified Clauss methods (Kamath and Lip, 2003). Direct methods, primarily methods that measure immunoreactive fibrinogen protein, are also available, and several have been developed for use with clinical samples. The immunologic methods have the advantage that they can be used with plasma prepared with a variety of anticoagulants (e.g., sodium citrate, EDTA), whereas the functional assays are most appropriately limited to plasma samples prepared with anticoagulants that have no impact on clottable fibrinogen, e.g., sodium citrate. Both the functional-based and immunologic-based methods can be calibrated against accepted international standards allowing for results from different laboratories, different methods, or different testing occasions to be properly compared (Whitton et al., 2000; Raut and Hubbard, 2010). For clinical studies, plasma fibrinogen concentration is typically measured in laboratories that adhere to accepted practices for the handling and testing of clinical samples and have well established and documented quality control processes for determining and monitoring assay performance. These assay methods were the subject of a literature review that was performed concurrently with these analyses.

Unpublished analyses have been conducted by industry to directly compare the fibrinogen results of samples tested using both the functional and direct assay methods, in order to identify an appropriate adjustment factor to account for the differences in fibrinogen results between these methods. Fibrinogen values for ECLIPSE have been corrected by -13.6% to account for the use of EDTA plasma instead of citrate plasma, based on data provided by the manufacturer of the assay used in ECLIPSE (Pacific Biometrics Inc., 2007).

## DESCRIPTIVE ANALYSES

### Objectives:

We will conduct several data validation steps to ensure the accuracy of the integrated dataset. UBC will attempt to reproduce patient counts from individual studies that have been either previously published in papers that give a clear description of the methods used to obtain those counts or data validation documents that have been released by the study coordinators. UBC will also note lab values that are out of range and verify these values with INC Research or the appropriate study coordinators.

These analyses will:

- Identify illogical, missing and out of range data values.
- Compare obtained counts with counts previously published or verified as accurate by the individual study coordinators to demonstrate reproducibility with source data.

Next, we will conduct univariate descriptive statistics on demographic and clinical information across all datasets and the integrated dataset. Although similar analyses may have been conducted previously in individual study datasets, the analytic population for the proposed analyses in this SAP may differ from the original studies. UBC will examine these sample descriptive statistics in each dataset and combined datasets, as they will be useful in future dissemination work to describe and characterize the patient population evaluated in subsequent analyses. Analyses will be performed among all patients included in the data, as well as those who meet the definition of COPD as previously described.

These descriptive analyses will:

- Identify important covariates
- Inform model development
- Characterize the study sample for use in future dissemination of research

### Proposed Analyses:

#### 1. Baseline characteristics

##### 1.1. Demographic characteristics

*Analyses:*

Compute descriptive statistics for baseline demographic characteristics in each dataset and combined datasets. Results will report missing values, as well as mean (SD), median, and range (minimum to maximum) for continuous variables and frequencies (count and percentage) for categorical variables. Certain variables of interest are only available in a limited number of studies in the integrated database; when applicable, the studies in which these variables are available are noted below.

*Variables:*

- Age
- Gender
- Race
- Ethnicity
- Weight
- Height
- Body Mass Index (BMI)
- Systolic blood pressure (SBP)/ Diastolic blood pressure (DBP)
- Smoking history
- Heart rate : ARIC, CHS, ECLIPSE
- Pulse: NHANES
- Blood oxygen saturation (SPo2): ECLIPSE
- Medical History
  - Including history of COPD
  - Including history of COPD exacerbations

## 1.2. Baseline clinical characteristics

*Analyses:*

Descriptive statistics for baseline clinical characteristics in each dataset and combined datasets will be computed. Results will report mean (SD), median, and range (minimum to maximum) for continuous variables and frequencies (count and percentage) for categorical variables. The distribution of fibrinogen will additionally be summarized using interquartile ranges and the geometric mean, to better describe the skewed nature of the data.

*Variables:*

- Plasma fibrinogen
- Spirometry

- Pre-bronchodilator Forced Expiratory Volume in 1 second (preFEV1)
- preFEV1 (% predicted)
- Pre-bronchodilator Forced Vital Capacity (preFVC)
- preFVC (% predicted)
- preFEV1/FVC ratio
- Post-bronchodilator Forced Expiratory Volume in 1 second (postFEV1)
- Post-bronchodilator Forced Vital Capacity (postFVC)
- postFEV1 (% predicted)
- postFVC (% predicted)
- postFEV1/FVC ratio
- COPD exacerbations
  - Hospitalization
  - Death
  - Reported exacerbation

## ASSESSMENT OF KEY ASSUMPTIONS

The use of this integrated dataset to accomplish the study objectives is predicated upon at least 2 assumptions:

1. Pre- and post-bronchodilator spirometric measurements each can be used to identify patients with COPD. Both measures are available only in the ECLIPSE and COPDGene studies. Utility of other studies requires the assumption that differences between pre- and post-bronchodilator measurements are not clinically important and that similar results are obtained using either method of defining COPD.
2. Most patients categorized at baseline as having 'high fibrinogen' maintain this classification during a period relevant to the conduct of a clinical trial.

### Objectives:

These analyses will:

- Compare COPD definitions using pre- and post-bronchodilator spirometric data within the ECLIPSE and COPDGene data.
- Assess longitudinal variation in plasma fibrinogen within individuals and between individuals using data from ECLIPSE.

## Analyses

### 1. Compare COPD definitions.

#### *Analyses:*

Two analyses are proposed to compare and validate the substitution of pre-bronchodilator spirometry measurements for post-bronchodilator measurements, which are recommended by GOLD but not available in all databases. First, we will compare patients categorized as having COPD using post-bronchodilator measurements (GOLD standard) with those classified as having COPD using pre-bronchodilator measurements. This analysis will permit calculation of error rates to determine the accuracy of using pre-bronchodilator measurements to define COPD in ECLIPSE. A similar analysis will be performed using data from the COPDGene study, which also collected pre- and post-bronchodilator spirometry measurements.

This comparative analysis of pre- and post-spirometry measurements will first include patients meeting the criteria for GOLD stage 2+ (FEV1/FVC <0.70 and FEV1 <80% of normal). We will compare the n and % of patients classified as having COPD by using the pre-bronchodilator spirometry data with those classified as having COPD using the post-bronchodilator spirometry data in studies with both measurement available. If pre-bronchodilator spirometry measurements are a reasonable proxy for post-bronchodilator measurements in patients with moderate to severe COPD, a similar n and % of patients will be categorized as having COPD when using either pre- or post-bronchodilator measurements. Misclassification (error) rates, sensitivity, and specificity will also be calculated for this analysis. Sensitivity analyses will be performed to assess whether error rates can be reduced by further restricting the sample of patients included in analyses to those with either FEV1 <70% of normal or FEV1 <60% of normal.

